The study physician will administer the assessment at all appointments. If the patient has a positive response characterized as “High Risk” as per the table, the study physician will take the appropriate clinical action, such as taking the patient to the emergency room, admitting the patient, or deciding to monitor them more closely. To maintain and improve patient safety, we are now formalizing the administration of the Columbia Suicide Severity Rating Scale (C-SSRS), an assessment used in Columbia University Irving Medical Center psychiatry clinical facilities including the Emergency Room. This will be documented in the patient’s chart. If responses to questions 1 and 2 in the 6-item scale are “no”, the rater skips to question 6. If the answer is “yes” to question 2, questions 3-6 are asked. Any “yes” on the scale indicates that someone should seek behavioral healthcare and the research team will ensure that this occurs. Further, if the answer to any of the items of 4, 5, 6 is “yes”, immediate action will be taken by the study physician, which involve the patient being taken to the Emergency Room or calling 911. This will be documented in the patient’s chart and an SAE will be submitted to the IRB. Based on the clinical situation, the study physician will decide, in conjunction with the study PI ([name]), if this should be reported as a Serious Adverse Event to the IRB, e.g., if the patient is hospitalized for suicidality. If the patient is hospitalized, the patient will be told to interrupt the study treatment, valacyclovir or placebo. Of note, there is no evidence that valacyclovir use is associated with increased suicidal ideation. If treatment interruption occurs, treatment with study medication can be resumed within 6 weeks (as per the protocol) if the patient no longer is deemed to be high risk for suicide based on repeat administration of the same suicide assessment that is used at CUIMC facilities. Non-clinical staff (e.g. research assistants) may become aware of suicide risk via routine phone calls and visits with the patient. If a non-clinical staff member is made aware of suicide risk they are required to immediately report suicide risk to the study physician available. There is a rotation for a study physician on call, which is constant each week, and when the study physician is not in, this authority is automatically delegated to [name] who is available 24/7. If the non-clinical staff member is made aware of the suicide risk outside of MDC clinic hours, they are required to report the suicide risk to [name], who is available for contact at all times (i.e., 24 hours/day, 7days/week). When [name] is not available he

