cholinesterase inhibitors and/or memantine throughout the duration of the study. Any changes to the medication will be documented in the participant research chart. Medications given for other medical reasons, e.g., antidiabetic or anti-hypertensive medications, will not be altered for the purposes of this trial and the patient's primary physician may adjust such medications as medically indicated throughout the trial. Psychotropic and other medications are allowed. Details of concomitant medication use will be documented at all visits and will be available for statistical analysis.	
7. Either PET amyloid scan positivity or prior CSF biomarker positive for AD (A β 42 and tau/p- tau).	Medical Records or through completing a PET Scan as part of screen
8. A family member, friend, or other individual who is in contact with the patient agrees to serve as the patient's informant during the study and signs the "Informant Information Sheet."	Patient Designation
Exclusion:	
1. Current clinical diagnosis of schizophrenia, schizoaffective disorder, other psychosis, bipolar disorder or current major depression by DSM-5 criteria. Prior history of major depression will not be exclusionary (25% of older adults have a lifetime history of major depression).	Physician Evaluation
2. Active suicidal intent or plan.	Physician Evaluation with SRMP Assessment
3. Current or recent (past 6 months) alcohol or substance use disorder (DSM-5 criteria).	Physician Evaluation
4. Current diagnosis of other major neurological disorders, including Parkinson's disease, multiple sclerosis, CNS infection, Huntington's disease, and amyotrophic lateral sclerosis.	Physician Evaluation
5. Clinical stroke with residual clinical deficits. MRI findings of cerebrovascular disease (small infarcts, lacunes, periventricular disease) in the absence of clinical stroke with residual neurological deficits will not lead to exclusion.	Physician Evaluation
6. Acute, severe, unstable medical illness. For cancer,	Physician Evaluation

patients with active illness or metastases in the last 12 months will be excluded, but past history of successfully treated cancer will not lead to exclusion.	
7. Sitting blood pressure > 160/100 mm Hg.	Physician Evaluation
8. Renal failure as determined by an estimated Glomerular Filtration Rate (GFR) < 44 ml/min/1.73m ² (see 4.3.b.).	Laboratory Report
9. Serum vitamin B12 levels below the normal range.	Laboratory Report

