If all aforementioned screening assessments and procedures are completed, and key inclusion criteria are met, the research coordinator will schedule screening 18F-Florbetapir PET scan only following confirmation of all key inclusion/exclusion criteria, as determined by PI and/or Study Physician.

SUVR > 1.15 (results reported within 5 days after scan) will be required for study entry. In our clinic and industry drug trials, PET amyloid scans and/or CSF is obtained to assess low A β 42 and high tau/p-tau with standard biomarker criteria for AD. If prior PET amyloid scan or CSF was AD-positive, the patient will be eligible, but will still have to complete an Amyloid PET scan at Baseline visit. Medical records will be required for verification if prior Amyloid PET and/or previous CSF AD Biomarker results are used to confirm study eligibility. If AD biomarker positive medical history cannot be confirmed, the Amyloid PET will take place as a screening procedure.

As part of the screening evaluation, a comprehensive history will be taken to include age, age-at-onset of memory problems, handedness, education, occupation, medical and psychiatric history.

As described in the consent forms, all clinically applicable information collected during the trial will be disclosed to patients, as well as interpretation of Baseline MRI and results from clinically relevant lab work and select neuropsychological testing.

After the Baseline evaluation, the results of outcome measures specified in the hypotheses will not be disclosed. Apolipoprotein E genotyping results will not be disclosed nor will results of viral proteome and antibody assays.

Throughout study weeks (baseline, weeks 0, 2, 12, 26 and 52), remote administration of measures (interviews and/or select neuropsychological testing) may be carried out. Research interviews and rating scales will be administered to the patient by the research coordinator and the study physician. These are done over the telephone prior to each clinic visit in order to minimize time spent in the clinic. Interviews and rating scales are done over the telephone because visual examination of the patient is not required. Clinic visits are necessary because neuropsychological testing and blood draws take place throughout protocol, and at specific visits, other procedures like MRI and PET are required.

BASELINE/WEEK 0 VISIT

Patients who are enrolled will be asked to come for the baseline visit, typically 1 week after the screening visit.

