An EKG will only be repeated at a patient's final study visit (Week 52) if they presented with an abnormality during their initial EKG.

Blood will be drawn for the following laboratory analyses: serum anti-HSV antibodies with quantitative IgG and IgM; HHV6A and HHV6B; HHV7; viral proteome and antibody assays; SMAC blood chemistry; Complete Blood Count; plasma biomarkers t- tau and NFL, and plasma acyclovir levels.

The following scans will be conducted: MRI and 18F-Florbetapir PET.

Patient will need to return all unused pills.

Time Line: The sample (N = 56) will be recruited over 52 weeks (1 year). After all patients complete the study, the blind will be broken, data analyzed, and manuscripts written. Data entry and cleaning will be done throughout the project and the dataset finalized concurrent with completion of patient participation.

Blindness of raters: Raters will remain blind to randomized treatment condition. The blind will not be broken during the entire trial. In a clinical emergency, the blinded medication (drug or placebo) will be continued if possible; if not, the blinded treatment will be stopped.

Diagnosis: diagnosis of MCI (includes eMCI and IMCI by ADNI criteria, defined by scores > 1 SD below norms on Logical memory II Story A Delayed Paragraph Recall: 9-11 if > 16 years of education, 5-9 for 8- 15 years of education, 3-6 for 0-7 years of education), HSV1 or HSV2 seropositivity, and either PET amyloid scan positivity or prior CSF biomarker positive for AD ($A\beta_{42}$ and tau/p-tau).

eMCI and IMCI:

Early MCI (eMCI) is a form a Mild Cognitive Impairment as is late Cognitive Impairment (IMCI). EMCI subjects represent individuals with milder degrees of cognitive impairment than the IMCI subjects. Both eMCI and IMCI are subtypes of Amnesic MCI. The difference is defined by patient performance on specific cognitive tests that are used to classify eMCI and IMCI.

IMCI is very similar to amnesic MCI by the original Petersen criteria. eMCI, less impaired than IMCI, was defined in ADNI, and a significant proportion of patients with eMCI decline cognitively, several of whom develop AD (Qiu et al. 2014). Therefore, we will include eMCI. Inclusion criteria for HSV seropositivity ensures targeting of patients who may respond to valacyclovir, and a positive PET amyloid scan (or CSF if done previously) increases the likelihood of AD neuropathology in this broadly defined MCI sample.

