Intent to Treat/ Dropouts and missing data: Dropout is estimated at 10% In patients who discontinue study medication, reason for early exit will be documented and study visits will continue at scheduled time- points per the Intent-to-treat (ITT) principle. The primary analyses will be on the ITT sample, i.e., all randomized subjects according to the treatment that they were assigned. Missing data on outcome variables will be dealt with by using (longitudinal) generalized linear mixed effects models that do not require complete measurements under the "missing at random" assumption. For MRI scan and 18F-Florbetapir PET scan, outcomes with just one pre and post measure, inverse probability weighting of cases with complete data will be used where weights are calculated based on the probability of a subject being a completer versus being a dropout. Sensitivity analysis will be performed to provide a range of plausible effect estimates that could arise due to non-ignorable missing data.

Treatment Interruption: treatment interruption for up to 6 weeks will be allowed for medical/surgical intervening conditions.

Data Safety and Monitoring Board (DSMB): A DSMB is required for this study; Drs. [name] (Chair), [name] (member) and [name] (member) are the individuals selected after consultation and approval from the NIA program staff. This procedure is required for pilot clinical trials in MCI and AD; we have done this before in our recent pilot clinical trials in mild cognitive impairment (MCI) and AD.

For each DSMB meeting or teleconference conducted at the start of the study and every (1) year thereafter, [name] who heads the database management team will provide the DSMB with a summary of study progress, SAEs and AEs. He will also provide unblinded data based on the DSMB's preference. The DSMB will make decisions about study continuation, monitor recruitment progress, AEs and SAEs, and provide recommendations to the project P.I. ([name]) and his team after each DSMB meeting or teleconference. NIA, and our IRB, will also be provided with the report sent by the DSMB Chair. If SAEs occur in > 10% of the first 20 patients, the DSMB will be approached so that they can guide the research team regarding study continuation.

Criteria for Early Discontinuation

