Prior to the submission of any study involving a faculty held IND or IDE being approved by the IRB, the IND/IDE holder is required to submit a [form](#) signed by the IND/IDE holder and PI.

Which are applicable to your study: ☒ Drug ☐ Device ☐ Radiolabeled drug/compound

Off Label and Investigational Use of Drugs

Enter the information for all drugs to be used in this study:

Name of the drug	Valacyclovir
Manufacturer and other Information	We will use the generic version of valacyclovir supplied to the NYSPI pharmacy.
Approval Status (select one)	IND application is pending IND is approved No IND is required
IND #	N/A.
Who holds the IND (i.e., IND Sponsor). If other than PI/CU Investigator, type name of holder.	N/A.
Which applies:	FDA has determined the IND is not required (provide correspondence) FDA conditions are met (see "Rules") – Explain https://www.fda.gov/drugs/investigational-new-drug-ind-application/ind-application-procedures-investigators-responsibilities

Protocol Summary Form

Off Label and Investigational Use of Devices

Enter the information for all devices to be used in this study:

Name of the device	
Manufacturer and other Information	
Approval Status (select one)	IDE application is pending IDE is approved No IDE is required
IDE #	
Who holds the IDE (i.e., IDE Sponsor). If other than PI/CU Investigator, type name of holder.	
Is the device marketed?	
Which applies:	FDA has determined that IDE is not required FDA conditions are met (see "Rules") – Explain https://www.fda.gov/medical-devices/investigational-device-exemption-ide/ide-application Device is "Non-significant risk" – Explain

Off Label and Investigational Use of Radiolabeled Drugs / Compounds

Enter the information for all radiolabeled drug/compounds to be used in this study:

Name of the radiolabeled drug/compound	18F-Florbetapir (Amyvid™)
Manufacturer and other Information	PETNET Solutions, Inc. Knoxville, TN 37932
Approval Status (select one)	IND application is pending

Protocol Summary Form

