Patients who experience any of these changes will be permitted to continue study participation.

Psychotropic and other medications will be permitted. Medication dosage of psychotropics may be changed during the trial if indicated by the patient's physician. All medication changes will be documented in the patient's study chart.

Common Side Effects: headache 14% drug versus 10% placebo, dizziness 2% drug versus 1% placebo in the largest placebo-controlled trial (n=609). Hallucinations, delirium and seizures occur in less than 1% of patients taking 2-4 g daily, and only in patients with renal failure. Valacyclovir at a high dose of 8 g daily in HIV led to SAEs in 10% of patients. Valacyclovir 3 g daily was efficacious in a randomized, double-blind, placebo-controlled, 18-week trial in 24 patients with schizophrenia with positive HSV1 titers, valacyclovir 3 g/day was superior to placebo with effect sizes of 0.79, 0.97 and 1.14 for tests of working memory, verbal memory, and visual object memory, respectively, from the computerized Penn battery (Prasad et al. 2013). Given the difficulty with achieving efficacy in MCI, we chose 4 g daily to ensure that we do not underdose while avoiding known toxicity associated with much higher doses. In our ongoing VALAD trial that targets a dose of 4 g daily, 2 of 76 patients have discontinued because of putative side effects (double-blind maintained, so they may be on drug or placebo), and 3 of 76 patients have continued at a lower dose of 2 or 3 g valacyclovir/placebo daily (2 g or higher is permitted). It is not uncommon for medical illness to lead to interruption of treatment, usually for short intervals (e.g., surgery). During the study, interruption of treatment with a visit delay for up to 6 weeks will be permitted. Treatment and data collection will resume after the interruption and the patient will continue in the protocol. All serious adverse events will be reported to our IRB and the DSMB.

Neuropsychological Assessment: During neuropsychological testing, some subjects may find some questions upsetting. The tester will discuss the situation with the patient and will allow for an expanded break between tests when feasible. If the patient still chooses not to proceed with testing, the patient's choice will be respected.

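### As worded, the blinding rule leaves no route to release one participant's allocation to a treating clinician in the rare emergency where it would affect urgent care

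*Protocol*

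**What the plan says.** The rule is in the protocol, Study Procedures, in the paragraph labelled Blindness of raters. After stating that raters stay blind, it says "The blind will not be broken during the entire trial". The next sentence covers emergencies: "In a clinical emergency, the blinded medication (drug or placebo) will be continued if possible; if not, the blinded treatment will be stopped". The Time Line paragraph just before it places unblinding after every patient has completed. The Data Management Plan limits data carrying treatment assignments to the DSMB until the database is locked. In the DSMB section, the head of database management has an unblinded role: "He will also provide unblinded data based on" the board's preference.

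On toxicity, Common Side Effects states: "Hallucinations, delirium and seizures occur in less than 1% of patients taking 2-4 g daily, and only in patients with renal failure". Exclusion criterion 8 removes such patients at entry: "Renal failure as determined by an estimated Glomerular Filtration Rate (GFR) < 44" (in ml/min/1.73m²).

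The SAP does not mention unblinding.

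**The concern.** A blinded drug trial normally lets a clinician treating an emergency obtain that one patient's allocation when the answer would alter treatment. Here the rule carries no exception, and the emergency sentence lists two actions, neither of which is disclosure. Someone following the paragraph literally would have to refuse such a request.

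What is at stake is the care of an individual in a rare event. The trial's inference is not in question. Valacyclovir is given at a target of 4 g daily to adults aged 50 to 95, and the protocol itself names CNS effects that it links to renal failure. In that setting a clinician could reasonably want to know whether the patient has been taking the drug.

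**Working it through.** This is a question of wording, so most of the check consists of setting the relevant places side by side. The only arithmetic is a headcount.

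**1. Does the rule reach beyond raters?** The label and the first sentence concern raters. Three things point to a trial-wide meaning. The Time Line paragraph uses the same term for the trial's allocation as a whole. The emergency sentence governs participants' medication, which raters do not control. The Data Management Plan separately keeps assignments from everyone but the DSMB until lock. The trial-wide reading is therefore the better supported one, though not the only possible one.

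**2. Is there another route to the allocation?**

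| Place in the protocol | What it allows | Route to a treating clinician? |
|---|---|---|
| Blindness of raters | Continue or stop, blinded | No |
| Time Line | Unblinding after all patients complete | No |
| DSMB | Unblinded data to the board if it prefers | No |
| Data Management Plan | Assignments to the DSMB only, until lock | No |
| Suicide Risk Management Plan | Interrupt study drug on hospitalization | No |

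No text available for this review, in either document, supplies one.

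**3. When is stopping blind enough?** The stated safety rules all work without the allocation:
- study drug is interrupted on hospitalization for suicidality;
- it is suspended for a heart rate over 100;
- the dose may fall to as little as 2 g daily for intolerance;
- it is reduced to 2 g and then stopped if serum creatinine stays above 1.5 mg/dl or eGFR below 44 mL/min.

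Stopping is safe in either arm, so these rules cover most emergencies.

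**4. What is left over?** Renal failure is excluded at entry only. Criteria for Early Discontinuation itself plans for kidney function to decline on study. A participant with new renal failure and new delirium or seizure would be in the setting that Common Side Effects ties to the drug. Stopping ends further exposure but does not tell the clinician whether the drug is a candidate cause. Plasma acyclovir is drawn for later analysis, so it gives no answer at the time. That knowing the allocation would sometimes alter treatment is a clinical judgement; no figure in the documents supports or refutes it.

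**5. How many participants could a changed rule still cover?** Inputs are from Summary of Experiences to Date: 56 planned, 24 completed, 3 who withdrew consent, 1 withdrawn by the study, 49 agreed to randomization.
- Withdrawn: 3 + 1 = 4.
- Remaining: 56 − 24 − 4 = 28.
- Cross-check: 49 − 24 − 4 = 21 in follow-up, plus 56 − 49 = 7 still to be randomized, gives 28.
- On valacyclovir, assuming an even split: 28 / 2 = 14.

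This is an upper bound, because anyone who finishes before the change takes effect drops out of it. No event probability is computed: the under-1% figure is confined to patients with renal failure, and the documents give no rate for patients who enter without it.

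**6. Would a release harm the analysis?** Both documents analyze participants as assigned, and the protocol follows those who stop study drug, so the analysis set is unchanged. Ratings need more care. Study staff who rate can stay blind if the release goes to the outside physician whom every patient must have. But the ADCS-ADL-PI, the Aim 3 outcome, is reported by the patient and by the study partner, and the CIBIC-Plus takes caregiver input. Any of these people could learn the allocation from the treating clinician.

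**The case against.** The strongest opposing case has four parts.

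- **Scope.** The paragraph is labelled for raters, and the sentence may simply continue that subject. This reading is possible but the weaker one, for the reasons given in the working. If it is what the authors meant, the same short edit would make it plain.
- **Unseen text.** Part of Study Procedures, between its opening and the imaging description, was not available for this review. It could cover randomization, dispensing or code-breaking. This stands in full. A reader might infer that the trial has no code-break procedure; the documents do not support that, and it is not claimed here.
- **No changed decision is shown.** The clinician can stop the drug and treat as if the patient had been exposed, and the protocol describes no arm-specific treatment. This also stands and is why the point is modest. A reader might go further and infer that the intervals between scheduled kidney tests strengthen the case. They do not: they concern laboratory monitoring, and a patient who presents in an emergency can be tested on arrival.
- **The remedy is not as simple as one sentence.** The Data Management Plan and Time Line would contradict it, self- and partner-reported outcomes could be affected, and round-the-clock cover is described only for study physicians, who should not see the code. These objections are right, and the fix is built around them.

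**Conclusion.** The concern holds in a limited form. As worded, the blinding paragraph gives a treating clinician no route to one participant's allocation, even where it would affect urgent care. Stopping the drug blind suffices in most emergencies. How often it would not suffice cannot be estimated from the documents. At most 28 participants, about 14 on active drug under an assumed even split, could still be covered by a change.

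The conclusion rests on two assumptions: that the rule is trial-wide, which the surrounding text favors, and that in some emergencies allocation would alter care, which is a clinical judgement. It does not rest on a code-break procedure being absent; if one exists, this paragraph conflicts with it and needs aligning. A reader might infer that participants are being managed unsafely. The documents do not support that: safety rules that work blind are in place, and renal failure is excluded at entry. This is an inexpensive improvement for a rare case.

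**What to change.** Add an exception to the sentence in Blindness of raters, along these lines: *except that one participant's allocation may be released to the treating clinician when it is needed for urgent care; each release is logged and reported to the DSMB; raters, outcome-rating study physicians and, where clinically possible, the participant and study partner stay blind; the participant stays in ITT follow-up.*

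Make these consequential changes:

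- Add a matching exception to the Time Line sentence and to the DSMB-only limit in the Data Management Plan.
- Name an existing non-rating role as code-holder. One candidate is database management, which already supplies unblinded data to the DSMB. The other is the pharmacy ("We will use the generic version of valacyclovir supplied to the NYSPI pharmacy"), although the protocol does not say that it holds the code.
- Make the code reachable out of hours, for example as a sealed or pharmacy-held code. The Suicide Risk Management Plan already has physician cover ("There is a rotation for a study physician on call, which is constant each week"). That physician should only relay the request, because under Screening Visit "Research interviews and rating scales will be administered to the patient by the research coordinator and the study physician".
- If a code-break procedure already exists elsewhere in Study Procedures, align this paragraph with it rather than adding a second one.

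The cost is a few lines of text, no new staff and a small on-call duty for the code-holder. A few participants may be individually unblinded. Some of their later ADCS-ADL-PI and CIBIC-Plus ratings may then come from people who know the allocation, and these should be flagged when results are reported.
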